Safety and Feasibility of Endoscopic Application of a Novel Therapy for Duodenal Mucosal Regeneration in the Treatment of Type II Diabetes (**REGENT-1 Study**)

Protocol number: **196**

Principal Investigator:

[name].
The Bariatric & Metabolic Institute
The BMI Clinic
[name]
[name]
[name]
Australia

Local Sponsor:

DyaMX Australia Pty Ltd
C/- Case Governance Pty Ltd
[name]
[name]
[name]
[REDACTED]

Medical Monitor

[name]
Division of Gastroenterology
Department of Internal Medicine
[name]
Baylor University Medical Center
[name], USA
[REDACTED]

Version O

30 Sep 2023

PREAMBLE

The REGENT-1 study is designed to assess the feasibility and preliminary safety of the Endogenex device for endoscopic duodenal mucosal regeneration in patients with type 2 diabetes (T2D) inadequately controlled on glucose-lowering medications. The protocol initially enrolled participants who were treated with non-insulin glucose-lowering agents. Following the enrollment of an initial group of participants supporting the safety and feasibility of the procedure, a second cohort is added to the study to assess the treatment in patients treated with basal insulin (referred as insulin cohort, IS cohort).

Insulin cohort participants will be treated with the same investigational device and procedure and be followed up according to the same follow-up schedule as described in the original protocol. For simplicity and clarity, the background medication management and their associated modifications to the inclusion/exclusion criteria, along with other necessary modifications in IS cohort are described in a protocol addendum (**Appendix 4**). The original protocol (#196), also referred as the “main protocol”, is kept unchanged. Participants enrolled under the main protocol will be referred as non-insulin (NIS) Cohort in study analysis and reports.

A second addendum to the protocol is added to enable longitudinal follow up of the participants beyond one year and the possibility of repeat treatment if clinically justified (**Appendix 5**).

TABLE OF CONTENTS

PREAMBLE	2
LIST OF ABBREVIATIONS	7
PROTOCOL SUMMARY	9
1 BACKGROUND	15
1.1 Type 2 Diabetes	15
1.2 Duodenal Mucosal Resurfacing	15
2 DEVICE DESCRIPTION	16
2.1 System Description	16
2.1.1 Generator and Controller	17
2.1.2 Catheter	18
2.1.3 Connecting Cables and Switchbox	20
2.2 Proposed Mechanism of Action	20
2.3 Proposed Indication	21

HbA1c	Glycosylated Hemoglobin
HDL	High-Density Lipoprotein
HOMA-IR	Homeostatic Model Assessment of Insulin Resistance
NIS Cohort	Non-insulin CohortIB Investigator's Brochure
ITT	Intent-to-Treat
IS Cohort	Insulin Cohort
LDL	Low-Density Lipoprotein
mITT	Modified Intent-to-Treat
NYHA	New York Heart Association
OAD	Oral Anti-diabetic Drug
PEF	Pulsed Electric Field
PP	Per Protocol

PPG	Post-prandial Plasma Glucose
SAE	Serious Adverse Avent
SGLT-2i	Sodium-Glucose Cotransporter-2 inhibitors
SoA	Schedule of Activities
SU	Sulphonylurea
T2D	Type 2 Diabetes Mellitus
TZD	Thiazolidinediones
UADE	Unanticipated Serious Adverse Device Effect

PROTOCOL SUMMARY

Protocol Title	Safety and Feasibility of Endoscopic Application of a Novel Therapy for Duodenal Mucosal Regeneration in the Treatment of Type II Diabetes (REGENT-1 Study)
Protocol Number	196
Investigational Device	Endogenex Device
Proposed Indication	The Endogenex Device is indicated for endoscopic treatment of small intestine in patients with type 2 diabetes inadequately controlled on glucose-lowering medications.
Regulatory Status	The device is under clinical investigation in Australia.
Objectives	The objective of this first-in-human study is to assess the feasibility and preliminary safety of the Endogenex device for endoscopic duodenal mucosal regeneration in patients with type 2 diabetes (T2D) inadequately controlled glucose-lowering medications.
Study Design	
This is a multicenter, single-arm, open-label study conducted in Australia.
 
Twenty (20) participants will be enrolled initially and up to 60 participants may be enrolled in the non-insulin (NIS) Cohort. The first 30 participants will be treated with the first-generation catheter (Gen 1) and the next 20-30 participants will be treated with the second-generation catheter (Gen 2). Patients who sign the informed consent and are deemed eligible following a general and endoscopic screening will be enrolled in the study.
 
Patients with T2D inadequately controlled on 1-4 non-insulin glucose-lowering medication(s) will be screened for study eligibility. Eligible patients who consent to participate in the study will maintain his/her background anti-diabetic medication(s) stable (no medication or dose change) for at least 12 weeks prior to baseline visit.
 
The index procedure will be performed under general anesthesia or deep sedation and within 28 days from the baseline visit. Patients will undergo an endoscopic screening immediately prior to the index procedure. The index procedure will be performed under fluoroscopic and endoscopic guidance. Patients may be discharged the same day per the local hospital's guideline. A patient is enrolled in the study when an energy delivery is attempted. Patients excluded during endoscopic screening will be considered screen failure and will be followed for four weeks after the procedure for safety.
 
Post index procedure, participant will be on a transitional diet consisting of clear liquids for 24 hours followed by full liquid diet for 3 days, pureed food for 3 day, and soft food for one week.
 
Background medication(s) may be decreased peri-procedurally per Section 6.2.2 but will be titrated to the pre-procedure dose and maintained for 24 weeks post index procedure and during the transitional diet period. After the 24-week follow-up visit, participants will be managed according to the current guidelines of American Diabetes Association and their glucose-lowering medications will be optimized to

	
achieve their individualized A1c goals, which for most individuals is a target of less than 7.0%.
 
Participants will receive lifestyle-modification counseling sessions at scheduled intervals to promote adherence to a healthy diet and a healthy lifestyle. The counseling will be provided by a member of the research team (endocrinologist, dietitian, nurse, etc.) trained in the delivery of lifestyle counseling for diabetes.

Patient Population	Male and female participants, 18-70 years of age, with T2D treated with 1-4 non-insulin glucose-lowering medication(s), and a HbA1C 58-97mmol/mol (7.5% - 11.0%), inclusive.
Primary Endpoint	Proportion of participants experiencing device- or procedure-related serious adverse events at 12 weeks post procedure.
Secondary Endpoints	
 • Procedure success rate defined as the proportion of participants who successfully received the target treatment of at least 6 cm of duodenum treatment • Procedure time defined as the time between the Endogenex catheter insertion and catheter removal. • Change from baseline in glycemic parameters post procedure by visits 
 ○ HbA1c ○ Fasting plasma glucose (FPG) ○ Insulin resistance by HOMA-IR ○ Post prandial plasma glucose (PPG), Beta cell function, disposition index by mixed meal tolerance test (MMTT) • Proportion of treated participants with an HbA1c improvement \geq0.3 points from baseline at 24 weeks • Proportion of treated participants with an HbA1c improvement from baseline at 24 weeks and maintained at 48 weeks • Change in weight from baseline by visit • Change in glucose-lowering medication usage • Change in liver enzyme from baseline at 24 weeks 
 ○ Alanine Aminotransferase (ALT) ○ Aspartate Aminotransferase (AST) • Change from baseline in blood pressure and lipid profile by visit
Safety Evaluation	Safety will be characterized through a summary of the incidence of adverse events, device-related adverse events, and serious device-related adverse events.
Inclusion Criteria	
 1. 18-70 years of age 2. Current diagnosis of T2D 3. History of T2D for less than or equal to 10 years 4. HbA1C of 7.5 -11.0% (58-97 mmol/mol), inclusive 5. BMI 24-40 kg/m², inclusive 6. On stable non-insulin glucose lowering medications (1-4 medications) for at least 12 weeks prior to baseline visit

	
 7. Weight stability (defined as a < 5% change in body weight) for at least 12 weeks prior to the screening visit 8. Agree not to donate blood during participation in the study. 9. Able to comply with study requirements and understand and sign the Informed Consent Form 10. Women of childbearing potential must be using an acceptable method of contraception throughout the study 11. Willing and able to perform self-monitoring blood glucose and comply with study visits and study tasks as required per protocol.
Exclusion Criteria	
 1. Diagnosed with type 1 diabetes 2. History of diabetic ketoacidosis or hyperosmolar nonketotic coma 3. Probable insulin production failure, defined as overnight fasting C-peptide serum <1 ng/mL (333pmol/l). 4. Previous use of any types of insulin for >1 month (at any time, except for treatment of gestational diabetes) in last 2 years. 5. Current use of insulin 6. Hypoglycemia unawareness 7. History of ≥ 1 severe hypoglycemia (defined by needing for third-party assistance), unless a clear correctable precipitating factor can be identified, in past 6 months from the screening visit 8. Known autoimmune disease, as evidenced by a positive anti-glutamic acid decarboxylase (GAD) test, including but not limited to celiac disease, or pre-existing symptoms of systemic lupus erythematosus, scleroderma or other autoimmune connective tissue disorder. (Participants with adequately controlled primary hypothyroidism may be included). 9. Previous GI surgery that has changed GI anatomy or could limit treatment of the duodenum, such as Billroth 2, Roux-en-Y gastric bypass, gastric band or other similar procedures or conditions. 10. Known history of a structural or functional disorder of the upper GI tract that may impede passage of the device through the upper GI tract or increase risk of tissue damage during an endoscopic procedure, including esophagitis, stricture/stenosis, varices, diverticula, or other disorder of the esophagus, stomach and duodenum. 11. Active H. pylori infection (Participants with active H. pylori may continue with the screening process if they are treated with an appropriate antibiotic regimen) 12. History of, or gastrointestinal symptoms suggestive of gastroparesis. 13. Acute gastrointestinal illness in the previous 7 days 14. Known history of irritable bowel syndrome, radiation enteritis or other inflammatory bowel disease, such as Crohn's disease and Celiac disease 15. History of chronic or acute pancreatitis. 16. Known active hepatitis or active liver disease other than NASH/NAFLD. 17. Alcoholic liver disease, as indicated by ANI > 0 and history of alcoholism 18. Current use of anticoagulation therapy (such as warfarin) that cannot be safely discontinued periprocedurally.

	
 19. Current use of P2Y12 inhibitors (clopidogrel, prasugrel, ticagrelor) that cannot be discontinued for 5 days before the procedure. 20. Unable to discontinue non-steroidal anti-inflammatory drugs (NSAIDs) during treatment through 4 weeks following the procedure. Use of acetaminophen and low dose aspirin is allowed. 21. Use of systemic glucocorticoids (excluding topical or ophthalmic application or inhaled forms) for more than 10 consecutive days within 12 weeks prior to the baseline visit. 22. Use of drugs known to affect GI motility (e.g. Metoclopramide) 23. Use of weight loss medications such as Meridia, Xenical, Phentermine or over-the-counter weight loss medications (prescription medication) 24. Persistent anemia, defined as hemoglobin <10 g/dL. 25. Known history of blood donation or transfusion within 3 months prior to the Screening Visit. 26. Known history of cardiac arrhythmia 27. Significant cardiovascular disease, including known history of valvular disease, or myocardial infarction, heart failure, transient ischemic attack, or stroke within 6 months prior to the Screening Visit. 28. Estimated glomerular filtration rate (eGFR) \leq 30 ml/min/1.73m². 29. Known immunocompromised status, including but not limited to individuals who have undergone organ transplantation, chemotherapy, or radiotherapy within the past 12 months, who have clinically-significant leukopenia, who are positive for the human immunodeficiency virus (HIV) or whose immune status makes the participant a poor candidate for clinical trial participation in the opinion of the investigator. 30. With any implanted electronic devices that can't be turned off during the procedure, or duodenal or biliary stent 31. Not a candidate for upper GI endoscopy or anesthesia. 32. Active illicit substance abuse or alcoholism (>2 drinks/day regularly) 33. Active malignancy within the last 5 years (excluding non-melanoma skin cancers) 34. Women breastfeeding 35. Participating in another ongoing clinical trial of an investigational drug or device. 36. Any other mental or physical condition which, in the opinion of the study investigator, makes the participant a poor candidate for clinical trial participation. 37. Critically ill or has a life expectancy <3 years 
Additional exclusion criteria to be confirmed during the screening process:
 
 38. HbA1c < 7.5% (58 mmol/mol) or > 11% (97 mmol/mol) at baseline visit 39. Any severe hypoglycemic event since the screening visit 40. Glucose level <54 mg/dl (3.0 mmol/l) in more than 1% of time by CGM since the screening visit 41. Uncontrolled hyperglycemia with a glucose level >270 mg/dl (>15 mmol/L) after an overnight fast or >360 mg/dl (>20 mmol/l) in a randomly performed
--	---

	
measurement that is confirmed by a second measurement (not on the same day) since screening visit
 
42. Mean of 3 separate blood pressure measurements >180 mmHg (systolic) or >100 mmHg (diastolic)
 
43. Women of child-bearing potential with a positive urine pregnancy test at baseline visit
 
44. LA Grade C or greater esophagitis on endoscopy
 
45. Abnormalities of the GI tract preventing endoscopic access to the duodenum
 
46. Anatomic abnormalities in the duodenum that would preclude the completion of the treatment procedure, including tortuous anatomy
 
47. Endoscopic observation of upper gastrointestinal abnormality such as ulcers, duodenal polyps in the area to be treated, varices, strictures, congenital or intestinal telangiectasia
 
48. Any other anatomical or endoscopic abnormalities/characteristics that, in the opinion of the investigator, would preclude safe use of the investigational device or procedure

Assessment Schedule	
 Visits: Screening, Baseline, Index Procedure, Week 1, Week 2, Week 4, and every 4 weeks thereafter Pancreatic enzyme: Baseline, Week 1 Glycemic parameters: Baseline, Week 4, 12, 24, 36, 48 Metabolic panel: Screen, Baseline, Week 1, 12, 24, 48 Fasting lipid panel: Baseline, Week 24, 48 Continuous blood glucose monitoring (CGM): Baseline, Day 1-Week 4, Week 12, 24, 36, and 48 Endoscopic follow up: Week 2-5 Diabetes review and medication titration will be performed by the treating physician at all visits (see Schedule of Activities)
Peri-Procedural Medications	
 Titration for Sulfonylureas and Meglitinides: 
 Dose reduction by 50% (or discontinuation if on the lowest recommended dose) starting on the day before index procedure through two-week transitional diet period post procedure. If a hypoglycemic episode is experienced (symptomatic or documented), the dose must be further reduced by 50% again or discontinued if the participant is on the lowest dose. Following the transitional diet period and a review of CGM readings, the medication will be returned to pre-procedure dose if deemed safe and appropriate by the principal investigator. Titration for other medications: 
 Metformin should be held the day prior to endoscopy and resumed post procedure when the patient tolerates oral intake. GLP-1 Receptor agonists should be held in the peri-procedure period if the subject experiences significant nausea and/or vomiting and can be resumed once symptoms resolve at the discretion of the principal investigator.

	
 ○ Generally, the dosage of other medications may remain unchanged peri-procedurally unless a hypoglycemic risk is identified by blood glucose monitoring. ● Proton Pump Inhibitor (PPI) 
 ○ Patients will be placed on PPI (Omeprazole 40 mg daily or equivalent) 1 week prior to the index procedure ● Antiemetics and antispasmodics 
 ○ Patients will be provided with antiemetics and antispasmodics on standby post procedure
Post Procedural Diet and Lifestyle Modification	
 ● Patient will be on clear liquid diet for 24 hours, followed by a full liquid diet for 3 days, pureed food for 3 days, soft food for one week, and then transitioned to normal diet as tolerated. ● Following the transitional diet period, patient will participate in monthly lifestyle modification counseling sessions to promote adherence to a diet and lifestyle suitable for diabetes.
Safety Monitoring	Safety will be monitored throughout the study. The investigators will assess the occurrence of adverse events at each follow up visit. An independent medical monitor will review and monitor the safety data throughout the study. Changes in amylase, lipase levels post procedure will be evaluated for any potential pancreatic injury.
Timeline	
 ● First Participant Enrolled: Q2 2021 ● Estimated Enrollment Duration: 24 months (Q2 2023) ● Last Participant to Primary Endpoint Follow-up: (Q2 2024) ● Study Duration: 36 months

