20. Unable to discontinue non-steroidal anti-inflammatory drugs (NSAIDs) during treatment through 4 weeks following the procedure. Use of acetaminophen and low dose aspirin is allowed.
21. Use of systemic glucocorticoids (excluding topical or ophthalmic application or inhaled forms) for more than 10 consecutive days within 12 weeks prior to the baseline visit.
22. Use of drugs known to affect GI motility (e.g. Metoclopramide)
23. Use of weight loss medications such as Phentermine, Meridia, Xenical, or over-the-counter weight loss medications (prescription medication)
24. Persistent anemia, defined as hemoglobin <10 g/dL.
25. Known history of blood donation or transfusion within 3 months prior to the Screening Visit.
26. Known history of cardiac arrhythmia
27. Significant cardiovascular disease, including known history of valvular disease, or myocardial infarction, heart failure, transient ischemic attack, or stroke within 6 months prior to the Screening Visit.
28. Estimated glomerular filtration rate (eGFR) \leq 30 ml/min/1.73m².
29. Known immunocompromised status, including but not limited to individuals who have undergone organ transplantation, chemotherapy, or radiotherapy within the past 12 months, who have clinically-significant leukopenia, who are positive for the human immunodeficiency virus (HIV) or whose immune status makes the participant a poor candidate for clinical trial participation in the opinion of the investigator.
30. With any implanted electronic devices that can't be turned off during the procedure, or duodenal or biliary stent

31. Not a candidate for upper GI endoscopy or anesthesia.
32. Active illicit substance abuse or alcoholism (> 2 drinks/day regularly).
33. Active malignancy within the last 5 years (excluding non-melanoma skin cancers)
34. Women breast feeding
35. Participating in another ongoing clinical trial of an investigational drug or device.
36. Any other mental or physical condition which, in the opinion of the study investigator, makes the participant a poor candidate for clinical trial participation.
37. Critically ill or has a life expectancy <3 years

Additional exclusion criteria to be confirmed during the screening process:

38. HbA1c < 7.5% (58 mmol/mol) or > 11% (97 mmol/mol) at baseline visit
39. Any severe hypoglycemic event since the screening visit
40. Glucose level <54 mg/dl (3.0 mmol/l) in more than 1% of time by CGM since the screening visit

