7.12.1 Screening Visit – Visit 1 (within 84 days from the Index Procedure)

To limit in-person visit, the screening visit may be performed remotely. Screening BMI eligibility will be based on self-reported height and weight. A screening consent may be used optionally to facilitate site-specific workflow. Potentially eligible participants will be scheduled for laboratory tests at the study laboratory. The following procedures/assessments will be performed during this visit:

- Informed consent prior to the conduct of any study-related procedures

- Inclusion and exclusion criteria
- Demographics
- Medical history including diseases, disorders and medications
- Diabetes history including diabetes medications
- Laboratory tests:
 - Hematology (CBC with differentials)
 - Metabolic panel (liver and renal function)
 - Fasting serum C-peptide
 - Anti-GAD
 - HbA1C
- H. Pylori (breath or stool test)
- Pregnancy test for females capable of becoming pregnant
- Registration on screening log

Once all data including testing results related to the screening have been obtained, the investigator will review the participant's eligibility for the study. If deemed eligible, participant will be scheduled for the baseline visit.

Eligible participant must meet all the inclusion criteria and none of the exclusion criteria with one exception. If a participant has met all other criteria except that s/he has been on stable glucose-lowering medication(s) for less than 12 weeks at the time of screening visit, the participant can be scheduled for baseline visit such that s/he will be on stable medication for 12 weeks at the time of baseline visit.

It is recognized that COVID-19 restrictions may cause delays in scheduling the index procedure, resulting in the screening visit being out of window. In case the screening visit is out of the visit window, the investigator will reassess the participant's eligibility by evaluating any changes in the participant's medical history and medications. The investigator may decide to repeat certain screening tests based on his/her medical judgement. If the investigator determines that the participant remains eligible for participating in the study, the participant may proceed to Baseline visit. Investigator's assessment and any repeated test results will be documented on eCRFs.

7.12.2 Baseline Visit – Visit 2 (within 28 days prior to the Index Procedure)

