4.1. Re-treatment Eligibility

Participants meeting the following criteria may be considered for re-treatment with the ReCET procedure:

- In NIS Cohort
- Treated with the Gen 2 catheter
- Has completed 48 weeks follow up
- Is sub-optimally controlled, defined as HbA1c $\geq 7.5\%$

- Had responded to the initial ReCET therapy, defined as HbA1c reduction of $\geq 1.0\%$ at any time after the initial ReCET procedure
- Consented to re-treatment and be followed up for at least one year after the re-treatment

In addition, the participant should **not have any of the exclusion criteria** listed in the main protocol with the exception of exclusion criteria # 4 and #5 (**Section 5.2 of the main protocol**).

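### Appendix 5 carries the visit-dated exclusions over to re-treatment without re-dating them, so nos. 21, 25, 38 and the timed clause of no. 27 do not test status before the repeat procedure.

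*Protocol*

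**What the plan says.** **Re-treatment rule.** Appendix 5 section 4.1 lists positive criteria, among them "Has completed 48 weeks follow up", HbA1c of at least 7.5%, and an earlier response. It then asks that the participant have none of the exclusions "listed in the main protocol with the exception of exclusion criteria # 4 and #5". It does not redefine any visit, and it does not import the inclusion criteria.

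**Criteria dated to a visit (main protocol 5.2, repeated in the Protocol Summary).**
- No. 27: "Significant cardiovascular disease, including known history of valvular disease", followed by a timed clause, "myocardial infarction, heart failure, transient ischemic attack, or stroke within 6 months prior to the Screening Visit".
- No. 25: "Known history of blood donation or transfusion within 3 months prior to the Screening Visit".
- No. 21: systemic glucocorticoids for more than 10 consecutive days in the 12 weeks before the baseline visit.
- No. 38: HbA1c below 7.5% or above 11% at the baseline visit.
- No. 39: "Any severe hypoglycemic event since the screening visit". Nos. 40 (CGM time below 54 mg/dl) and 41 (confirmed hyperglycemia) also run from the screening visit.

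**The visits.** The only Screening and Baseline visits defined are Visits 1 and 2, both before the index procedure (7.12.1, 7.12.2, Appendix 2). Appendix 5 Table 2 has a *Before Re-Treatment* column at day -28 to -1, but nothing equates it with either visit.

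**The concern.** The sponsor went through the exclusion list for re-treatment, since it lifted nos. 4 and 5, but left the reference dates where they were. A look-back that ends at a visit held about a year or more ago says nothing about the months before the second procedure.

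Three things are at stake. Section 5 states the aim of enrolling people without significant cardiovascular conditions. The procedure is done under general anesthesia or deep sedation (6.1). Appendix 5 section 4 says no data exist on the safety or efficacy of re-treatment. That is where an objective rule, applied alike at every site, is worth most.

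Nos. 21, 25 and 38 also bear on the measurements. HbA1c decides who may be re-treated, and its change after re-treatment is an Appendix 5 endpoint. I assume nos. 21 and 25 serve partly to protect glycemic readings; the protocol gives no reason for them.

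**Working it through.** No sample size or error rate is involved. The check is date arithmetic, then a sorting of the criteria by anchor.

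**Inputs.** The index procedure is day 0. Screening is at day -84 to -5 and baseline at day -28 to -1 (Appendix 2). The two may be combined inside the baseline window (7.12.2). Re-treatment comes after 48 weeks, 48 × 7 = day 336 (Appendix 5, 4.1). Follow-up runs to month 24 ± 14 days (Appendix 5, Table 1). One month is taken as 30.4375 days, and 6 months as about 183 days.

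**Formula.** Gap from the end of the look-back to re-treatment = (day of re-treatment) + (days from the anchor visit to the index procedure).

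| Anchor and timing of re-treatment | Calculation | Gap |
|---|---|---|
| Screening, day 336 | 336 + 5 to 336 + 84 | 341 to 420 days (11.2 to 13.8 months) |
| Combined screening and baseline at day -1, day 336 | 336 + 1 | 337 days (11.1 months) |
| Screening, month 24 + 14 days | 730 + 14 + 5 to 730 + 14 + 84 | 749 to 828 days (24.6 to 27.2 months) |
| Baseline (nos. 21, 38), day 336 | 336 + 1 to 336 + 28 | 337 to 364 days (48.1 to 52.0 weeks) |

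If a Week 48 visit held 7 days early counted as completed follow-up (an assumption), each day-336 figure falls by 7. The smallest becomes 329 + 1 = 330 days. Late screening lengthens the gap, and 7.12.1 allows it: "In case the screening visit is out of the visit window, the investigator will reassess the participant's eligibility by evaluating any changes".

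**Against the look-back lengths.** Every gap exceeds the 6 months of no. 27, the 3 months of no. 25 and the 12 weeks of no. 21. With screening at day -5 and re-treatment at day 336, the 6 months before re-treatment begin 341 - 183 = 158 days after the window of no. 27 has closed. The two periods do not overlap.

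**Sorting the criteria at re-treatment, read as written.**
- *Fixed at first entry:* nos. 21, 25, 38 and the timed clause of no. 27.
- *Running forward from the first screening:* nos. 39 to 41, now spanning about 11 to 27 months. For nos. 39 and 41, a qualifying event at any time in that span excludes. No. 40 is a share of CGM time, so its denominator also grows.
- *No gap:* no. 7 (severe hypoglycemia in the 6 months before screening), because no. 39 covers everything after screening. No. 39 lacks the allowance in no. 7 for a correctable precipitating factor.
- *Not tied to a visit, still in force:* no. 26 (arrhythmia), no. 31 (not a candidate for endoscopy or anesthesia), no. 36 (investigator judgement), no. 37 (critically ill), and the head term of no. 27.

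**HbA1c.** With no. 38 fixed at the first baseline visit, the only HbA1c limit left at re-treatment is the floor of 7.5% in section 4.1. The 11% ceiling has no current measurement to act on.

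**Review of history.** Appendix 5 section 4.3.1 lists changes in medical history among the evaluations before re-treatment. Table 2 marks that item only at Month 12/Exit.

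**The case against.** The strongest reply is that section 4.1 orders a fresh application of the exclusions and Table 2 schedules an eligibility check at day -28 to -1, so the sponsor plainly meant the criteria to be read from that check. This is plausible. It is not written, however, and the protocol defines no other Screening or Baseline visit. Two sites could apply the same sentence differently.

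The second reply concerns the consequence. A reader might infer that a recent infarction or stroke is no bar to a repeat procedure. The documents do not support that. Nos. 26, 31, 36 and 37 and the untimed head term of no. 27 can each exclude such a person. Appendix 5 section 4 requires the investigator to weigh changes in medical condition and whether the procedure is still appropriate. This part of the reply stands. These are judgements, though, and do not replace the dated criterion set for first entry.

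A reader might also extend the point to the index procedure, since nos. 25 and 27 stop at screening. Section 7.12.2 reconfirms eligibility at baseline and removes a participant whose condition has changed. Re-dating the criteria there would be a preference, not a correction.

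**Conclusion.** The point holds for four criteria: nos. 21, 25, 38 and the timed clause of no. 27. As written, their reference date lies about 11 months to more than 2 years before the repeat procedure, and the HbA1c ceiling lapses. Nos. 39 to 41 work the other way and accumulate from the first screening. It would therefore be wrong to infer that the timed exclusions as a group can exclude nobody.

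What is lost is the objective timed bar. The conclusion rests on the literal reading, in which the Screening and Baseline visits are Visits 1 and 2. If the sponsor intended otherwise, the defect is one of wording, and the remedy is the same.

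Two limits on size. The exact minimum gap depends on the visit windows, but no case above comes near 6 months. And not every cardiovascular serious adverse event after re-treatment would enter the re-treatment safety endpoint, because Appendix 5 section 2 counts only device- or procedure-related events.

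**What to change.** 1. Add one sentence to Appendix 5 section 4.1: for re-treatment, the Screening Visit and baseline visit named in nos. 21, 25, 27 and 38 mean the *Before Re-Treatment* assessment (Table 2, day -28 to -1), with the existing look-back lengths unchanged and counted from that single date.
2. Have the sponsor state from which visit nos. 39 to 41 run at re-treatment. For nos. 39 and 41 a later start would admit some participants who are now excluded; for no. 40 the effect could go either way. That choice should be made openly. If no. 39 is moved, no. 7 needs the same reference date, or severe hypoglycemia in between may fall under neither.
3. Reconcile section 4.3.1 with Table 2 on when changes in medical history are reviewed.

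No change is needed for the index procedure.

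The cost is eligibility wording in the next amendment. The history-based criteria need no new tests, and HbA1c is already scheduled before re-treatment. A few re-treatment candidates may be deferred or excluded. Up to 28 days between the assessment and the procedure would still rest on investigator judgement.
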